4.1.4. Summary of Clinical Studies

Study B03CS was a phase 1, double blinded, placebo controlled, 2-period, incomplete crossover study conducted in 16 healthy adult subjects to investigate the safety, tolerability, and pharmacodynamics of ADV7103.

Since the active principles of ADV7103 are endogenous substances and homeostatic mechanisms are fully functional in healthy adult subjects, it was not possible to determine the pharmacokinetic profiles of ADV7103 constituents and to evaluate their effects in the blood. Therefore, the main objective was to assess pharmacodynamic effects on urine pH of oral doses of ADV7103 after 5 days of treatment. It has been demonstrated that ADV7103 produces alkalization of the urine over at least 8 hours, which supports a dosing frequency limited to

2 times a day. The observed safety profile of ADV7103 was favorable: only 4 adverse events that may be attributed to the IP were observed (2 headache, 1 vertigo, and 1 nausea), and no serious adverse event occurred during the study. Contrary to current alkalinizing agents that are associated with frequent gastrointestinal side effects, only one episode of nausea of mild intensity was observed after administration of the highest dose of ADV7103 (50/100 mg/kg of ADV7103 (ie, approximately 100 mEq of alkali load) for a total of 240 doses without meals. Moreover, no hyperkalemia was observed when blood samples were obtained 2 hours after ADV7103 intake.

Thus, this phase 1 study demonstrated a favorable safety and tolerability profile for ADV7103 with urine alkalinizing effects of a duration that supports twice daily dosing. Improved gastrointestinal tolerability relative to other alkalinizing agents was apparent. Additional details are presented in the ADV7103 investigator's brochure (IB).

A phase II/III multicenter, open-label, non-inferiority, sequential study (B21CS) was conducted in order to evaluate the efficacy, safety, tolerability and acceptability of ADV7103 compared to the standard of care (SOC) in pediatric and adult subjects with dRTA.

Thirty-two (32) subjects have completed the study, including 7 adults, 8 adolescents (12-17 years old), 14 children (4-11 years old) and 3 infants (0.5-3 years old). Thirty (30) of them have been fully evaluable.

The subjects participated in three consecutive study periods:

- First Study Period (SP I) of 5 days: the subjects receive their current alkali treatment so called Standard of Care (SOC);

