4.3.1. Known and Potential Risks

The risks related to potassium citrate and potassium bicarbonate are primarily gastrointestinal (GI) adverse events (AEs) and hyperkalemia with potential cardiac consequences. The proposed prolonged-release formulation (ADV7103) should allow avoiding both GI intolerance and significant hyperkalemia, as already demonstrated during the Phase I B03CS study in healthy subjects. Data from the B21CS and B22CS studies do not indicate major risks related to hyperkalemia.

The required doses of ADV7103 in this study are anticipated to be lower than the maximal recommended intake of potassium per day (Mandal, 1997; EFSA, 2006). Electrolyte balance is tightly regulated and adaptive to exogenous intake via homeostatic mechanisms. The renal elimination of potassium increases and reabsorption decreases with increased potassium intake in healthy kidneys (Hannedouche, 2007). Patients with hypokalemic dRTA typically require potassium supplementation in addition to alkalizing therapy. Subjects with severe renal impairment are excluded from this study.

Females of childbearing potential can be enrolled in the study. The reproductive toxicity studies show no teratogenic or embryotoxic/fetotoxic effects of various forms of citrate (refer to ADV7103 IB). In a clinical study, 46 pregnant cystinuric subjects treated with sodium bicarbonate and potassium citrate continued treatment throughout pregnancy with no effect on the fetus (Gregory, 1983).

Risks associated with dRTA subjects receiving placebo (representing withdrawal of alkalinizing agent and potassium supplement) include development of metabolic acidosis and its associated clinical manifestations, hypokalemia, as well as allergy or intolerance to components of the placebo formulation. All subjects in the Withdrawal period will be closely monitored, with frequent monitoring of serum bicarbonate and potassium levels to minimize potential risks of acidosis and hypokalemia.

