6.2.3. Period 3 (Randomized, Double-blinded Withdrawal)

As soon as practicable following Visit 2, eligible subjects taking their pre-randomization dose of ADV7103 will enter Period 3 (Visit 3) randomization for an adequate period to monitor serum bicarbonate and potassium levels in the context of randomized, double-blinded treatment withdrawal. Period 3 start and randomization may occur in the evening prior to the first dose of blinded study product the next morning or early in the morning prior to the first dose of blinded study product. The duration of this efficacy assessment period (ie, Visit 3) will be approximately 6 days initially. The duration may be adjusted if approved by a bDMC following review of data from a subset of at least 8 subjects to complete Period 3 (see details in [Section 11.8.2](#)). The final

study day of this period may be less than 24 hours in duration with discharge occurring after the evening dose and required data collection.

After baseline evaluations including laboratory tests are completed, subjects will either continue their stabilized ADV7103 dose or switch to a weight-matched identical-appearing placebo dose according to their randomized treatment assignment (without potassium supplementation). In the unexpected situation where these Period 3 baseline evaluations disclose a serum bicarbonate level < 18 mEq/L for subjects ≥ 4 years old and < 17 mEq/L for subjects < 4 years old and/or a serum potassium level < 3.0 mEq/L for all subjects, the subject will not be dosed with blinded study product. Rather, at the Investigator's discretion, the subject may receive open-label ADV7103 or a SOC regimen to address these abnormal laboratory results. When the clinical status of the subject allows, the subject will be discharged from Period 3 with instructions to continue open-label ADV7103 or a SOC regimen and within 4 weeks to complete Visit 4 study exit evaluations.

The Investigator and staff (except for the pharmacist) will be blinded to Period 3 study product assignments, but not to laboratory results. The subjects will remain blinded to treatment throughout Period 3. In all subjects, serum bicarbonate and potassium levels will be measured every 24 hours following administration of the first dose of blinded study product (or more frequently if deemed necessary for safe subject management) through the remainder of Visit 3.

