6.3.2. Secondary Endpoints

- Proportion of subjects with 2 consecutive serum bicarbonate levels below the LLN for age during the Withdrawal Period;
- Proportion of subjects developing new onset hypokalemia during the Withdrawal Period. Hypokalemia is defined as a serum potassium level < 3.5 mEq/L.
- Time to metabolic acidosis during the Withdrawal Period;
- Time to new onset hypokalemia during the Withdrawal Period;
- Proportion of subjects with both metabolic acidosis and new onset hypokalemia during the Withdrawal Period;
- Mean urinary calcium/creatinine ratio associated with Visit 1, Visit 2;
- Mean change in urinary calcium/creatinine ratio during the Withdrawal Period;
- Mean urinary citrate/creatinine ratio associated with Visit 1, Visit 2;
- Mean change in urinary citrate/creatinine ratio during the Withdrawal Period;

- Frequency and severity of all adverse events (AEs), TEAEs, and all study product-related AEs;
- Frequency of SUSARs;
- Frequency of hyperkalemia;
- Frequency of serum potassium levels < 3.0 mEq/L;
- Frequency of serum potassium levels < 3.5 mEq/L;
- Changes in other serum and urine safety laboratory results from SOC baseline;
- Frequency of urine pH > 8.5 in Periods 1, 2, and 3.

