10.2.11.2. Serum Chemistry

A serum chemistry panel will be obtained in association with Visit 1. During Period 3, a serum chemistry panel will be obtained prior to the first dose of blinded study product and on the last day of Period 3. In the event of early study withdrawal by a subject following at least 4 weeks of study participation, a serum chemistry panel will be obtained in association with the Early Withdrawal Visit.

The serum chemistry panel will include the following analytes (at a minimum): sodium, potassium, chloride, bicarbonate/total carbon dioxide, blood urea nitrogen, serum creatinine, glucose, calculated eGFR, aspartate transaminase, alanine transaminase, total bilirubin, alkaline phosphatase, calcium, phosphorus, magnesium, and uric acid. These samples will be analyzed and reported by the central laboratory (ACM Global Laboratories).

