10.2.11.6. Serum Bicarbonate and Serum Potassium

Blood samples will be collected for the measurement of serum bicarbonate and serum potassium levels during Period 2 as specified in [Section 6.2.2](#), with attention paid to proper blood volume limitations for pediatric subjects. During Period 3, samples will be collected pre-dose (AM) for the first 24 hours following administration of the first dose of blinded study product and every 24 hours thereafter unless the Investigator determines that additional sampling is necessary for safe management of the subject ([Section 6.2.3](#)). Blood samples will also be collected for the measurement of serum bicarbonate and serum potassium levels in association with Visit 4.

Samples for measurement of serum bicarbonate will be analyzed within 2 hours after obtaining the sample.

In the event a blood sample appears hemolyzed to any degree, another sample should be collected as soon as possible for measurement of a serum potassium level. If the degree of hemolysis is severe, another sample should be collected as soon as possible for measurement of a serum bicarbonate level, too.

Utilizing whole blood samples (0.1 cc), an electrolyte panel (Cl⁻, K⁺, Na⁺, tCO₂) will be prepared by a qualified delegate/nurse for measure of serum bicarbonate and serum potassium, analyzed and reported at point-of-care via the portable iSTAT System (Abbott Inc.).

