10.3.3. Period 3 (Randomized, Double-blinded Study Product Withdrawal)

Period 3 study visits will take place at the subject's home, via telehealth (audio/visual supported virtual visit) or if preferred and feasible at the investigator's site, on an outpatient/ office-level basis.

10.3.3.1. First Full Day in Period 3

The following procedures and assessments will be conducted in association with the first full day of Period 3:

- vital signs prior to the first dose of blinded study product ([Section 10.2.4](#)), and again later in the day;
- targeted physical examination prior to the first dose of blinded study product ([Section 10.2.6](#));
- begin cardiac monitoring prior to the first dose of blinded study product ([Section 10.2.9](#))
- hematology panel prior to the first dose of blinded study product ([Section 10.2.11.1](#));
- serum chemistry panel prior to the first dose of blinded study product ([Section 10.2.11.2](#));
- spot urine collection ([Section 10.2.11.3](#));
 - Urine samples will be collected during the second void of the day. This second void of the day follows the first study product dose of the day (ie, morning dose); the first void of the day (not collected) precedes the first study product dose of the day. The second daily urine sample will be collected within 30 minutes prior to the second study product dose of the day.
 - The urine sample collected during the first full day of Period 3 will be used for microscopic analysis and dipstick testing for determination of pH, as well as to provide SS CaOx, SS CaP, and SS uric acid results.
- serum bicarbonate and serum potassium ([Section 6.2.3](#) and [Section 10.2.11.6](#));
 - blood samples will be collected every 6 hours for the first 24 hours following the first dose of study product unless the Investigator determines that additional sampling is necessary for safe management of the subject.
- serum pregnancy test, prior to administration of blinded study product (if applicable; [Section 10.2.11.7](#));
- concomitant medications prior to the first dose of blinded study product ([Section 10.2.13](#));

- adverse events ([Section 10.2.14](#));
- collect unused ADV7103 prior to first dose of study product ([Section 10.2.19](#)); and
- administration of blinded study product just prior to the morning and evening meals/snacks/feedings ([Section 10.2.18](#)).

10.3.3.2. Remaining Days in Period 3

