ⁿ Please refer to [Section 10.2.11.3](#) of this protocol for additional important details. During each full day of Period 3, two spot urine samples will be collected. The first of 2 daily urine samples will be collected during the second void of the day. This second void of the day follows the first study product dose of the day (morning dose); the first void of the day (not collected) precedes

the first study product dose of the day. The second daily urine sample will be collected within 30 minutes prior to the second study product dose of the day (evening dose).

^o During Visit 1, subjects will be given instructions for 24-hour urine collection and, where appropriate, supplies for 24-hour collection. During Visit 2, the investigational site team should confirm that the second 24-hour urine collection was completed and sample sent to Litholink.

^p The 24-hour urine collections (a total of 2) will not take place at each remote interaction. Rather, the first of two 24-hour urine collections will take place in association with Visit 1 (ie, following Visit 1 during a remote interaction), and the second 24-hour urine collection will be completed during or prior to Visit 2 (ie, via a remote interaction) during the Stabilization Phase of Period 2. In cases where 24-hour urine collections are not feasible, spot urine samples will be requested. All other remote interactions will NOT involve a 24-hour urine collection.

^q Results to be determined within 2 hours after blood sample collection. During Period 2, blood sample collection should be prior to the morning dose of ADV7103. In the event a blood sample appears hemolyzed to any degree, another sample should be collected as soon as possible for measurement of a serum potassium level. If the degree of hemolysis is severe, another sample should be collected as soon as possible for measurement of a serum bicarbonate level, too.

^r Following first dose of blinded study product. The sampling frequency may be adjusted if the Investigator determines that additional sampling is necessary for safe management of the subject.

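### Routine potassium sampling is mainly pre-dose, so the hyperkalemia endpoint is largely a trough measure and cannot exclude post-dose hyperkalemia; the Period 3 sampling text also conflicts

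*Combined protocol and SAP*

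**What the plan says.** **Risk and endpoint.** Section 4.3.1 names two primary risks: gastrointestinal events and "hyperkalemia with potential cardiac consequences". Section 6.3.2 lists "Frequency of hyperkalemia" as a secondary endpoint, and section 5.2 asks for new-onset hyperkalemia by period and, in Period 3, by arm. Neither gives a threshold or a sampling time.

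**Period 2.** The Study Schedule footnote reads "During Period 2, blood sample collection should be prior to the morning dose of ADV7103". Section 6.2.2.1 says the same for titration samples.

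**Period 3.** Section 10.2.11.6 says "samples will be collected pre-dose (AM) for the first 24 hours following administration of the first dose of blinded study product and every 24 hours" afterwards. Section 6.2.3 says "serum bicarbonate and potassium levels will be measured every 24 hours following administration of the first dose of blinded study product"; because that first dose is a morning dose, this is again the next pre-dose time. Section 10.3.3.1 differs: on the first full day "blood samples will be collected every 6 hours for the first 24 hours following the first dose of study product". The table in 17.1 differs again: every 6 hours for 24 hours, then every 8 hours.

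**Untimed samples.** A chemistry panel, which includes potassium, is drawn "prior to the first dose of blinded study product and on the last day of Period 3" (10.2.11.2). The last-day draw has no stated time relative to dose, and neither does the Visit 4 sample.

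**Earlier data.** In phase 1, "no hyperkalemia was observed when blood samples were obtained 2 hours after ADV7103 intake" (section 4.1.4).

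**The concern.** A pre-dose sample suits bicarbonate control and hypokalemia, where the question is whether the effect lasts to the end of the dosing interval. It is poorly placed to detect a rise after a potassium load. If nearly all potassium values on ADV7103 are pre-dose, a low or zero hyperkalemia count describes potassium at that time only. A clinical study report that gives the count without saying so invites the conclusion that ADV7103 does not cause hyperkalemia at any time in the dosing interval, although the later hours are the only part that was routinely sampled.

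**Working it through.** The plan states no figure for hyperkalemia, so there is none to reproduce. Its sample-size statement (12.1) concerns acidosis and is unaffected.

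**1. Period 2.** Titration lasts 1 to 4 weeks with a sample every 2 to 4 days: 7/4 ≈ 2 up to 28/2 = 14 samples. Stabilization lasts 6 to 8 weeks with a sample every 2 weeks: 6/2 = 3 up to 8/2 = 4. All are pre-dose, and no text conflicts. Period 2 lasts 7 to 12 weeks, against about 6 days in Period 3 and up to 4 weeks in Period 4, so it holds most of the ADV7103 exposure.

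**2. Period 3.** Set the first morning dose at t = 0, with doses at 0, 12, 24 h and so on, and count scheduled samples through the Day 6 morning (t = 120 h). A sample is off-trough if t is not a multiple of 12.

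| Text | Sample times (h) | Samples | Off-trough |
|---|---|---|---|
| 6.2.3 and 10.2.11.6 | 24, 48, 72, 96, 120 | 5 | 0 |
| 10.3.3.1, then 10.3.3.2 | 6, 12, 18, 24; 48 to 120 by 24 | 4 + 4 = 8 | 2 (6 h post-dose) |
| 17.1 table | 6, 12, 18, 24; 32 to 120 by 8 | 4 + 12 = 16 | 10 (4, 6 or 8 h post-dose) |

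None has a sample 2 to 3 h after a dose.

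**3. Other required samples.** Section 6.2.3 requires a potassium repeat at 2 to 4 h if the value is below 3.5 mEq/L or has dropped by more than 15%. It also requires a bicarbonate repeat within 2 to 4 h of a value below the acidosis limit, and the point-of-care panel reports potassium too. Such repeats can fall after the morning dose, but only in subjects selected for low or falling values. A hemolyzed sample is simply redrawn. No rule prompts a further sample for a high potassium.

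**4. Where 12 h falls in release.** Section 9.1.1 gives release over 2 to 3 h for citrate and about zero-order release over 10 to 12 h for bicarbonate. Section 9.2 gives 267 mg and 527 mg per 8 mEq sachet. With assumed formula weights of 324.4 (three potassium) and 100.1:

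- citrate potassium: 3 × 267/324.4 = 2.47 mEq; bicarbonate potassium: 527/100.1 = 5.26 mEq; total 7.73 mEq, of which citrate is 32%
- released by 3 h: (2.47 + 5.26 × 3/12)/7.73 = 49%, or with 3/10, 52%
- early to late release rate, taking citrate release as constant: lowest (2.47/3 + 5.26/10)/(5.26/10) = 2.6; highest (2.47/2 + 5.26/12)/(5.26/12) = 3.8

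A 12 h sample is thus at or just after the end of release. This is release from the granules, not serum potassium.

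**5. What a zero count would mean.** Let p be the true incidence of post-dose hyperkalemia and s the share still visible at the sampled time, both assumed. P(no case seen) = (1 − ps)^n.

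| n, p | s = 1 | s = 0.5 | s = 0.25 | s = 0.1 |
|---|---|---|---|---|
| 16, 10% | 18.5% | 44% | 67% | 85% |
| 16, 20% | 2.8% | 18.5% | 44% | 72% |
| 40, 10% | 1.5% | 13% | 36% | 67% |

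With no case seen, the one-sided 95% upper limit is 1 − 0.05^(1/n): 17% for n = 16 and 7% for n = 40. That limit applies only to potassium at the sampled time.

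**6. Can the under-count be sized?** Take potassium as normal with SD 0.4 mEq/L, trough mean m, post-dose rise d and threshold c (all assumed). P(exceed) = 1 − Φ((c − m − d)/0.4).

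| m, c (mEq/L) | d = 0 | d = 0.3 | d = 0.5 | d = 0.8 |
|---|---|---|---|---|
| 4.2, 5.0 | 2.3% | 10.6% | 22.7% | 50% |
| 3.7, 5.0 | 0.1% | 0.6% | 2.3% | 10.6% |
| 4.2, 5.5 | 0.1% | 0.6% | 2.3% | 10.6% |
| 3.7, 5.5 | <0.1% | <0.1% | 0.1% | 0.6% |

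The answer runs from under 0.1% to 50% depending on inputs that the documents do not give. The size is unknown.

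**The case against.** There is a good case that this matters little. Two current passages (10.3.3.1 and the 17.1 table, which section 10.1 calls the complete schedule) still require off-trough samples in Period 3. Most of the potassium is in a near zero-order component, which should flatten any peak. Phase 1 saw no hyperkalemia at 2 h. Section 4.3.1 says that prolonged release should avoid significant hyperkalemia and that the two earlier dRTA studies show no major risk. Investigators may add samples, cardiac monitoring runs in Period 3, the unblinded monitoring committee sees laboratory and cardiac data, and continued up-titration for low potassium requires potassium to stay at or below 5.0 mEq/L.

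Much of this stands. The Period 3 part is conditional on how the text is reconciled, and the pharmacology favours a small peak-to-trough difference. But the phase 1 subjects were 16 healthy adults, in whom section 4.1.4 says homeostasis is fully functional. The text available for review does not say when potassium was sampled in the earlier dRTA studies. Monitoring protects subjects; it does not count hyperkalemia. Period 2 is untouched by the conflict.

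A reader might infer that no post-dose potassium is required anywhere. The 6-hourly and 8-hourly text and the low-value repeats contradict that. A reader might also infer that hyperkalemia is the main named risk; section 4.3.1 names it together with gastrointestinal events.

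**Conclusion.** The point holds in limited form. In Period 2, and in Period 3 if sections 6.2.3 and 10.2.11.6 govern, every routinely timed potassium sample on ADV7103 is drawn about 12 h after the last intake. The endpoint is then mainly a trough measure and cannot exclude post-dose hyperkalemia. In Period 3, off-trough scheduled samples number 0 of 5, 2 of 8 or 10 of 16 depending on which passage is followed. These counts assume doses exactly 12 h apart.

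A reader might go further and conclude that the trial will miss hyperkalemia or that its safety result will be falsely reassuring. The documents do not support that: they contain no serum potassium time course, no peak-to-trough difference and no hyperkalemia threshold. A missed rise is possible, not shown. The endpoint is a descriptive safety endpoint, and the primary analysis is not affected.

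**What to change.** 1. **Reconcile the Period 3 sampling text** in 6.2.3, 10.2.11.6, 10.3.3.1, 10.3.3.2 and the 17.1 table. Which schedule stands is for the sponsor to decide.
2. **Define and label the endpoint.** In 6.3.2 and the safety analysis (12.4), state the hyperkalemia threshold and record time since last dose for every potassium value. Report pre-dose and post-dose results separately, call the former *pre-dose (trough) hyperkalemia*, and state that it does not exclude post-dose hyperkalemia. This is needed whatever the true size, and it is the only remedy here for Period 2.
3. **Time one existing draw.** In 10.2.11.2, give the planned last-day Period 3 panel a fixed, recorded time after the morning dose, which section 8.3 already has directly observed; phase 1 sampled at 2 h. Report its potassium descriptively by product actually received at that time.

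Item 3 cannot serve as a placebo comparison. Subjects who reach acidosis restart ADV7103 (6.2.3), and at the planned 85% rate that is 16 × 0.85 = 13.6 of 16 placebo subjects, leaving about 2 on placebo. The panel is also run by the central laboratory while the other potassium values are point-of-care, so the report should note the assay difference.

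**Cost:** protocol wording, a time field on each potassium record, a short wait by the nurse on one day, and a slightly narrower safety claim. No blood draw is added.
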